8.3.7 Adverse events based on examinations and tests

The results from the clinical study protocol mandated laboratory tests and vital signs will be summarized in the clinical study report (CSR). Deterioration as compared to baseline in protocol mandated laboratory values and/or vital signs should therefore only be reported as AEs if they fulfill any of the SAE criteria or are the reason for discontinuation of treatment with the IP or are considered to be clinically relevant as judged by the investigator (which may include but not limited to consideration as to whether treatment or non-planned visits were required or other action was taken with the study treatment, e.g. dose adjustment or drug interruption). Clinically relevant deteriorations in non-mandated parameters should also be reported as AE(s).

If deterioration in a laboratory value/vital sign is associated with clinical signs and symptoms, the sign or symptom will be reported as an AE and the associated laboratory result/vital sign will be considered as additional information. Wherever possible the reporting Investigator uses the clinical, rather than the laboratory term (eg, anemia versus low hemoglobin value).

Deterioration of a laboratory value, which is unequivocally due to disease progression, should not be reported as an AE/SAE.

Any new or aggravated clinically relevant abnormal medical finding at a physical examination as compared with the baseline assessment will be reported as an AE unless unequivocally related to the disease under study (DUS), see Sections 8.3.9 and 8.3.10.

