9.3.3 Endpoint measures for analyses

9.3.3.1 Calculation or derivation of safety variables

Safety and tolerability will be assessed in terms of AEs (including SAEs), deaths, laboratory data, vital signs, and exposure (ie, durvalumab monotherapy or combination therapy). These will be collected for all patients. “On treatment” will be defined as assessments between date of start dose and 90 days following discontinuation of IP (ie, the last dose of durvalumab in combination

with any other approved or investigational anticancer agents or durvalumab monotherapy). For AEs, on treatment (or treatment-emergent AEs) will be defined as any AEs that started after dosing or prior to dosing and which worsens following exposure to the treatment. For the change from baseline summaries for vital signs, laboratory data, and physical examinations, the baseline value will be the latest result obtained prior to the start of study treatment, or the date of enrollment if the patient is not to receive study treatment (Cohort 3). The denominator in vital signs data should include only those patients with recorded data.

AEs observed up until 90 days following discontinuation of durvalumab will be used for the reporting of the AE summary tables. Any AEs in this period that occur after a patient has received subsequent anticancer therapy will be flagged. Reporting and collection of late onset toxicity after the 90-day period is described in Section 8.3.2.

More details will be provided in the SAP.

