5.2.5 Safety

Safety data will be summarized according to the treatment received for the SAS (all patients who received at least 1 dose of durvalumab either as continuation of study treatment or retreatment in this study, and inclusive of patients who received the last dose of durvalumab or durvalumab combination from the parent clinical study within 90 days of enrollment [all cohorts]). AEs, vital signs, dose at time of AE, and laboratory safety assessments (clinical chemistry, hematology and thyroid stimulating hormone [reflex free triiodothyronine or free thyroxine]) will be listed individually by patient.

The number of patients experiencing each AE will be summarized by study cohort and CTCAE grade (v5.0). Each patient will be represented with the maximum reported CTCAE grade for each system organ class / preferred term. Number (%) of patients with AEs, will be sorted by international System Organ Classes (SOC) order and alphabetical PT and then maximum grade. Event rate per 100 patient-years will also be calculated for each AE.

Individual laboratory measurements and vital signs data will be presented in listing format.

For laboratory measurements, the following data will be listed:

- Subject identifier and cohort
- Age/sex/race
- Analysis visit
- Category of lab test
- Lab test examination name

- Result/finding
- Units
- Reference range indicator

For vital signs, the following data will be listed:

- Subject identifier and cohort
- Vital signs test name
- Analysis visit
- Result
- Unit
- Result clinically significant (yes/no)
- Reference ranges (upper and lower limits).

For vital signs, the following reference ranges and units will be used:

- For Diastolic blood pressure: Range = 40-110, Unit = mmHg
- For Heart rate/Pulse: Range = 50-120, Unit = beats/min
- For Respiratory rate: Range = 12-35, Unit = breaths/min
- For Systolic blood pressure: Range = 60-160, Unit = mmHg
- For Temperature: Range = 35-39, Unit = °C / Range = 95-102.3, Unit = °F
- For Weight: Range = 30-140, Unit = Kg / Range = 66-308, Unit = LB
- Oxygen saturation: 95-100%, unit-free.

Note: Based on an “as needed” request from parent clinical studies, safety data from WAVE may be combined with parent study data in order to update safety summaries.

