7 CHANGES OF ANALYSIS FROM PROTOCOL

There are no changes to the analyses specified in the version of protocol that this SAP is based on.

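### Protocol 8.3.7 limits AE reporting of laboratory and vital-sign deteriorations because the CSR will summarise them, but protocol 9.3.1 and SAP 5.2.5 specify only listings

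*SAP*

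**What the plan says.** Protocol 8.3.7 opens with a commitment: "The results from the clinical study protocol mandated laboratory tests and vital signs will be summarized in the clinical study report (CSR"). It derives the AE reporting rule from that commitment. When a mandated laboratory value or vital sign worsens from baseline, the rule is that such changes "should therefore only be reported as AEs if they fulfill any of the SAE criteria or are the reason for discontinuation of treatment". The treatment meant is the investigational product (IP). A third condition admits changes that "are considered to be clinically relevant as judged by the investigator". Where symptoms accompany the change, "the sign or symptom will be reported as an AE and the associated laboratory result/vital sign will be considered as additional information".

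Protocol 9.3.3.1 also takes summaries for granted: "For the change from baseline summaries for vital signs, laboratory data, and physical examinations, the baseline value will be the latest result obtained prior". The cut-off is the first dose of study treatment, or enrollment for Cohort 3.

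The analysis sections plan something else. Protocol 9.3.1 has laboratory and vital-sign data listed patient by patient and counts only AEs, by cohort and CTCAE grade. SAP 5.2.5 does the same: "Individual laboratory measurements and vital signs data will be presented in listing format". It sets out the fields of each listing. SAP 7 then declares: "There are no changes to the analyses specified in the version of protocol that this SAP is based on".

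**The concern.** The restriction in protocol 8.3.7 is a reasonable trade. Sites need not turn every out-of-range value into an AE, because the values will be tabulated elsewhere. The trade works only if that tabulation exists. Here the restriction stays and the summary it relies on is not specified.

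The primary objective is long-term safety. The AEs of special interest in protocol 8.3.13 include transaminase, creatinine, and lipase and amylase increases, and thyroid disorders, all of which can show as laboratory changes. If the plan is followed exactly, whether a high-grade laboratory value is counted depends on an open-label investigator's view of its clinical relevance, and no table of measured values stands beside the AE table as a check.

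**Working it through.** The plan states no figure on this point and no arithmetic applies. The check is a comparison of sections, followed by tracing where a deterioration can end up.

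**1. What each section provides for laboratory and vital-sign data**

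| Section | Provision |
|---|---|
| Protocol 8.3.7 | Summary in the CSR, given as the reason for limiting AE reporting |
| Protocol 9.3.3.1 | Change-from-baseline summaries assumed; baseline defined |
| Protocol 9.3.1 | Patient listings; only AEs are counted |
| SAP 5.1 | Generic descriptive statistics; baseline and change from baseline defined |
| SAP 5.2.5 | Patient listings; only AEs are tabulated |
| SAP 7 | No departure from the protocol declared |

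The conflict is therefore inside the protocol (8.3.7 and 9.3.3.1 against 9.3.1) and carries through to the SAP.

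**2. What the listings hold**

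The laboratory listing in SAP 5.2.5 has identifier and cohort, age/sex/race, visit, test category, test name, result, units and a reference-range indicator. It has no CTCAE grade, no baseline value and no change from baseline. The vital-sign listing has the result, reference limits and a clinical-significance flag, but again no baseline or change. The baseline definitions in protocol 9.3.3.1 and SAP 5.1 are used by no laboratory or vital-sign output in SAP 5.2.5.

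**3. Where a deterioration goes under protocol 8.3.7**

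- It meets SAE criteria, is the reason for stopping the IP, or is judged clinically relevant: it becomes an AE, with or without symptoms, and enters the AE tables by cohort and maximum grade and the rate per 100 patient-years.
- It comes with clinical signs or symptoms: the sign or symptom is the AE and is tabulated; the measured value is supporting information.
- None of these applies: it is not an AE and appears only as rows in a listing.

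Only the third group is absent from every specified summary. A Grade 3 or 4 value can fall in it, because numerical grade is not among the reporting conditions. (Protocol 8.3.7 separately excludes laboratory deterioration unequivocally due to disease progression. That exclusion has its own reason and this point does not depend on it.)

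**4. Which tables the collected data can support**

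- Values, units and reference ranges go on the eCRF (protocol 8.1.1), so grading needs no new collection.
- Protocol Tables 2 and 3 schedule no laboratory sample at enrollment for patients off treatment, and the parent-study data lists (protocol 8.2.1, SAP Table 2) include no laboratory results. A shift from baseline is therefore not generally available for patients not dosed in WAVE.
- Cohort 1 patients are already on durvalumab at entry (inclusion criterion 5), so their baseline is not a pre-durvalumab state.

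**The case against.** **The SAP does not forbid summaries.** SAP 5.2.5 begins by saying that safety data will be summarised, SAP 3.2 counts laboratory data and vital signs among the safety assessments, and SAP 5.1 applies descriptive statistics to all variables where appropriate. This is true, but the wording is generic. The specific instruction for these two data types is listings with named fields, and that is what a programmer would produce.

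**The SAP follows protocol 9.3.1.** This stands. The fault is not the SAP's alone, and its no-changes statement is accurate against 9.3.1. It is not accurate against 8.3.7 and 9.3.3.1.

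**No defined endpoint is lost.** The laboratory component of the primary endpoint is limited to findings that qualify as an SAE or AE (protocol Table 4, SAP 1.1). This also stands. It means, however, that the endpoint passes through the same reporting rule, whose stated justification is the missing summary.

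**Serious liver cases are already covered.** Protocol 8.1.1 and 8.3.8 route combined elevations to evaluation and, where criteria are met, to SAE reporting. A biochemical count would supplement that process. It would not recover an otherwise invisible signal.

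**Stronger readings.** A reader might infer that sites are told to withhold most deteriorations, or that no asymptomatic abnormality reaches a safety summary. The documents support neither. The clinical-relevance route is open-ended and may include values that needed treatment, an unplanned visit or a drug interruption, and none of the three reporting conditions requires symptoms. A reader might also conclude that laboratory toxicity will be under-reported by a material amount. The documents show a route by which that can happen and say nothing of how often.

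**Rewording the protocol would also end the contradiction.** Bringing 8.3.7 and 9.3.3.1 into line with a listings-only plan, and recording it in SAP 7, would make the text consistent. It would leave the third group uncounted and the AE restriction without its stated reason.

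**Conclusion.** The point holds in a limited form and should be acted on. Protocol 8.3.7 and 9.3.3.1 rely on summaries that protocol 9.3.1 and SAP 5.2.5 do not specify. Deteriorations that are not serious, do not lead to IP discontinuation, are not judged clinically relevant and have no reportable symptom enter no specified safety summary, including any Grade 3-4 values among them.

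The number of patients affected cannot be derived from the documents. It could be zero if investigators judge every such value relevant; nothing in the documents sets an upper figure. No hypothesis test, error rate or sample size is involved, since the study is descriptive. For a descriptive study with safety as its primary objective, however, the tables are the result.

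The conclusion assumes that sites apply 8.3.7 as written and that outputs are confined to those named in SAP 5.2.5. Table shells outside these two documents could already contain the summaries; if so, the SAP should name them.

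**What to change.** In SAP 5.2.5 add, for the safety analysis set up to 90 days after the last dose:

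1. Tables of baseline to worst CTCAE v5.0 grade for the gradable parameters in protocol Tables 9 and 10, for Cohort 1 and retreated Cohort 2, with a note that the Cohort 1 baseline is taken at WAVE entry on prior durvalumab.
2. Worst post-entry grade only, for patients not dosed in WAVE.
3. Number (%) of patients with AST or ALT at least 3 x ULN together with total bilirubin at least 2 x ULN, labelled as a biochemical count alongside the existing Hy's law SAE reporting.
4. The vital-sign change-from-baseline summary that protocol 9.3.3.1 presupposes.

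Add the CTCAE grade to the laboratory listing. Align protocol 9.3.1 with 8.3.7 and 9.3.3.1 so that all three describe the same outputs.

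The cost is SAP wording, a protocol clarification and a modest set of standard tables. No new data are needed. The main effort is harmonising units and reference ranges, because all results come from local laboratories.

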5.2.6 Demographics and baseline characteristics

The following will be summarized for all patients in the FAS by treatment group (cohort 1, cohort 2, cohort 3). Continuous variables will be summarized by the number of observations, mean, Sd, median, upper and lower quartiles minimum, and maximum. Categorical variables will be summarized by frequency counts and percentages for each category:

- Patient disposition (including screening failures) and inclusion in analysis sets
- Demographics (age, age group [<50 , $\geq 50 - < 65$, $\geq 65 - < 75$ and ≥ 75 years], sex, race, ethnicity, and country)
- Subject recruitment by clinical parent study (for each parent study; the study design, code, total number of patients in parent study and in WAVE study)
- Patient recruitment by country and by center

- Patient characteristics at baseline (height, weight, BMI)
- Disease characteristics at baseline (ECOG performance status, primary tumor location)
- Extent of disease at baseline: locally advanced/metastatic, site of disease

5.2.7 Concomitant and other treatments, and concomitant procedures

All concomitant and other treatment, and concomitant procedures data will be listed in the FAS, using Anatomical Therapeutic Chemical (ATC) classification and ATC coding. Missing coding terms will be listed and summarized as "Uncoded".

5.2.8 Exposure

Exposure to durvalumab treatment will be summarized for the SAS, only in Cohort 1 and Cohort 2 (retreatment). Mean, Sd, median and ranges will be produced for the following summaries:

- Summary of duration of exposure of study treatment (total treatment duration (months), actual treatment duration (months)),
- Summary of delays in study treatment cycles as well as reasons of delays,
- Summary of dose intensity:
 - RDI defined as the percentage of the actual dose delivered relative to the intended dose through treatment discontinuation
 - Percent intended dose defined as the percentage of the actual dose delivered relative to the intended dose through progression.
- Cumulative exposure over time.

5.2.9 Subsequent therapy

Cancer therapy post-discontinuation of durvalumab will be summarized in the FAS. For each cohort, the number (%) of patients will be summarized by tumor location and anticancer regimen.

6 INTERIM ANALYSES

No interim analysis has been planned for this study.

7 CHANGES OF ANALYSIS FROM PROTOCOL

There are no changes to the analyses specified in the version of protocol that this SAP is based on.

9 APPENDIX

9.1 List of AESI

The following AESI are listed in the current version of eCRF:

- Potential Endocrinopathies
- Potential Hepatic Events
- Potential Nephritis or Renal Dysfunction
- Potential Neuropathy/Neuro-muscular Toxicity
- Potential Pancreatitis
- Potential Rash or Dermatitis
- Potential GI Toxicity
- Potential Myositis/Polymyositis
- Potential Myocarditis
- Other (to be specified in EDC)

SIGNATURE PAGE

This is a representation of an electronic record that was signed electronically and this page is the manifestation of the electronic signature

Document Name: D910FC00001-sap-v2-ed		
Document Title:	Statistical Analysis Plan - Version 2 - Edition	
Document ID:	CCI [REDACTED]	
Version Label:	3.0 CURRENT LATEST APPROVED	
Server Date (dd-MMM-yyyy HH:mm 'UTC'Z)	Signed by	Meaning of Signature
02-Dec-2022 13:35 UTC	PPD [REDACTED] (Cytel Inc)	Content Approval
02-Dec-2022 13:42 UTC	PPD [REDACTED]	Content Approval

CCI [REDACTED]
